14.5 STOP THE STUDY

At the discretion of the Principal Investigator of this study, the study may be terminated at any time for medical reasons. In addition, the Sponsor reserves the right to stop the study at any time if it cannot be conducted in accordance with the protocol.

In the event of premature termination or suspension of the study, the study sponsor will promptly inform the investigator and the authorities. All study materials should be returned, destroyed or retained as directed by the sponsor.

14.6 ARCHIVING

Study documents must be archived by the participating center in a dedicated, access-controlled area for a period of 15 years, to ensure the confidentiality and protection of personal data collected during the study. The standard archiving procedures of the investigating center will be applied.

15 DOCUMENTATION AND USE OF STUDY RESULTS

All information related to this study and not yet published is confidential and remains the sole property of the Sponsor. The physician agrees to use this information only for the conduct of the study and for no other purpose except with the prior written consent of the Sponsor, except for possible communications to representatives of the relevant health authorities.

A report of the study will be written at the end of the study and will be submitted to the Scientific Committee for review and approval.

All study data and results are the sole property of the Sponsor.

Communications at scientific meetings and publications in peer-reviewed scientific journals will be made under the cover of the Scientific Committee which will validate their form and content in agreement with the Sponsor.

16 SCHEDULE OF THE STUDY

The projected schedule for the study is as follows:

- Regulatory submissions: October 2019
- Obtaining regulatory approvals: December 2019
- Implementation of the study: January to October 2020
- Patient Inclusion: January 2020 to November 2020
- End of follow-up of the last patient: March 2021
- Database freeze: June 2021
- Full study report with follow-up: December 2021

However, the total duration of the study or the recruitment period may vary depending on regulatory deadlines and recruitment capacities.

1 ABBREVIATIONS

ANSM	National Agency for the Safety of Medicines and Health Products
CRA	Clinical Research Associate
ATC	Anatomical, Therapeutic and Chemical Classification
CRO	Company Provider (Contract Research Organization)
eCRF	Electronic Case Report Form
UE	Undesirable Event
SAE	Serious Adverse Event
SD	Standard deviation
EVA	Visual Analog Scale
BMI	Body Mass Index
ITT	Intent to Treat
LPPR	List of Reimbursable Products and Services
NSN	Number of subjects needed
PDM	Personal Diabetes Manager
РР	Per Protocol
РТ	Preferred Term
SNITEM	National Union of the Medical Technology Industry
SOC	Organ system class

The purpose of this document is to detail the statistical analyses that will be performed for the MedInPS study, based on the study protocol (Final Version 1.3, dated May 13, 2020). This document was drafted by the statistician, and reviewed and approved by the study sponsor prior to the baseline freeze.

2 RATIONALE FOR THE STUDY

The treatment of patients with type 1 and type 2 insulin-requiring diabetes is based on insulin therapy that mimics the physiological secretion of the pancreas through a basal/bolus regimen, obtained either by multi-injections or by pump. The objective of this basal/bolus regimen is to approach normoglycemia in order to prevent :

- in the long term, chronic complications of diabetes;

- in the short term, acute complications of diabetes which are metabolic emergencies (including coma): related either to hyperglycemia \pm ketoacidosis or hypoglycemia.

Diabetes is a serious disease because of its complications. However, these complications can be prevented and/or mitigated with sustained metabolic control of blood glucose. This control aims to achieve an A1c level of less than 7 or 7.5% (the percentage being different depending on the recommendation and the type of patient) without increasing hypoglycemic episodes. A position paper from the Société Francophone du Diabète published in 2009 states that external insulin pumps have proven effective for years as an intensive treatment of diabetes by improving glycemic control and reducing hypoglycemia.

Overall, the indications for pump therapy can be summarized as follows:

- need for an intensive program (at least 3 injections per day, 3 self-monitoring of blood glucose per day);

- poor glycemic control despite intensive treatment (A1c > 7.5%, 2 episodes of severe hypoglycemia or unexplained coma within a year and/or 4 moderate hypoglycemia per week);

- variability of insulin requirements.

Absolute contraindications are rare and include severe psychiatric disorders, rapidly progressing ischemic or proliferative retinopathy (prior to laser treatment), and high magnetic field exposure.

In the current decades, there have been several innovations in diabetes management. Pumps have become smaller, less invasive and easier to use. They also have the potential to have sensors and algorithms built into them to be part of a loop that should lead, in the longer term, to an artificial pancreas.

In addition, the latest models of so-called "patch-p pumps" can detect an early occlusion resulting in the absence of insulin infusion. All pumps are built with an occlusion alarm, but it often goes off too late on conventional pumps. The long catheters of conventional pumps have some elasticity, which means that they can expand, storing insulin and thus delaying the moment of "hyperpressure", which is triggered only when 5 to 7 units of insulin have not been administered. This delay can be dangerous, especially for children. In the new patch pump design, this alarm is more immediate in case of occlusion, due to the absence of a catheter.

Today, in France, there are two types of insulin pumps for continuous external subcutaneous infusion (CSII):

1. The so-called "durable" insulin pumps (also called "conventional") which deliver insulin continuously using a tube and an external catheter. These models are listed on the LPPR (Liste des Produits et Prestations Remboursables) on a generic line. The LPPR provides for the reimbursement of insulin pumps and consumables by means of complete packages. The conditions for registration of portable insulin pumps and associated services are set by decree.

2. External insulin pumps, called "patch pumps", which cannot be reused and are designed without external tubing. These patch pumps also deliver insulin continuously, but the insulin delivery system itself is not durable and is managed by a remote control - a PDM (Personal Diabetes Manager). This type of device does not include external tubing and does not require the installation of a catheter. The insulin delivery reservoirs adhere to the skin with an adhesive patch that lasts 3 days. They are changed regularly but do not require long-term maintenance. The absence of tubing reduces the number of catheter and tubing incidents (skin tolerance, obstruction). In addition, they allow for early detection of occlusion and these systems are lighter, allowing for less clutter and more daily comfort. These models are listed on the LPPR under their own name (brand).

The LPPR provides for the reimbursement of insulin pumps and services associated with their installation, monitoring and training. The conditions for registration of insulin pumps and associated services are also set by decree.

The available epidemiological data do not allow for a precise determination of the target population. According to CNAMTS databases from 2019, the number of patients using an external insulin pump was estimated at 82,000.

Insulin pump administration has a different penetration rate depending on the type of diabetes and the age group (estimated penetration rate in adults: 16%, in children: 50%).

3 OBJECTIVES OF THE STUDY

3.1 MAIN OBJECTIVE

The primary endpoint is the estimate of HbA1c at 3 months based on mean blood glucose measurements over the past 10 weeks for each pump use.

The patient's average blood glucose over the past 10 weeks was calculated in each arm from measurements automatically recorded by a continuous glucose sensor that the patient was already using: the FreeStyle Libre.

3.2 SECONDARY OBJECTIVES

Secondary objectives were to describe the following information:

- HbA1c values measured at the medical and biological laboratory at the beginning and end of the study
- Glucose measurements (minimum, maximum, mean/median, standard deviation, out-of-target value, time in range, variability)
- Glycemic events (hypoglycemia and hyperglycemia as defined by the ADA, coma, other complications)

- Skin and general tolerance
- Technical incidents with the device
- Overall patient satisfaction, in the overall population and in each arm
- Insulin treatment compliance

4 METHODOLOGY

4.1 GENERAL SCHEME OF THE STUDY

This is a longitudinal, randomized, comparative interventional study of type 1 or 2 diabetic patients requiring insulin treatment delivered by a patch pump. The study is multicenter in France, prospective, randomized in two parallel groups 1:1, open-label, with a non-inferiority methodology versus a comparator device (Omnipod® pump marketed by the company Insulet and which is already reimbursed in France since 23/02/2016).

It was planned that 75 type 1 or 2 diabetic patients would be included in the study by 8 hospital centers specialized in diabetes.

In order to facilitate the recruitment of patients already using an Omnipod® pump to be randomized into the Omnipod group (thus without changing their pump), it was proposed that these patients could use a Medtrum pump at the end of the study for 1 month. Thus, all patients in the study had the opportunity to use the new A7+ TouchCare® pump.

The expected duration of the study was: 1 month of set-up, 3 months of patient recruitment, 12 weeks of follow-up per patient, 1 additional month for patients in the Omnipod group to test the Medtrum pump, 3 months of data management, i.e. approximately 11 months of study.

4.2 STUDY POPULATION

4.2.1 Patient selection

The investigating centers had to propose participation in the study for each patient potentially eligible for the study according to the inclusion and non-inclusion criteria.

Each patient had to be informed by the investigator orally and in writing by means of the information leaflet informing them of the objectives and modalities of the study, of the collection and computer processing of their health data, of their right to withdraw from the study without having to justify themselves. The patient had the possibility to ask questions to the study staff of the investigating center. If a patient decided to participate, he/she had to sign the consent form approved by the Ethics Committee before any procedure related to the study.

A patient was included in the clinical study only after giving written informed consent and meeting all inclusion criteria and none of the non-inclusion criteria.

Because the patients in this study were not involved in emergency medical treatment, no consent was collected in this specific emergency setting.

4.2.2 Selection of centers

The study was carried out in France, 8 hospital centers specialized in diabetes were asked to participate in the study.

4.3 INCLUSION OF PATIENTS

4.3.1 Inclusion criteria

To be included in the study, all patients had to meet all the following inclusion criteria:

- Patient with type 1 or type 2 diabetes, 18 years of age and older
- Patient already equipped with an Omnipod[®] insulin patch pump (Insulet) and a FreeStyleLibre sensor (Abbott)
- A1c between ≥6.5% ≤9.5%
- Treated with any type of rapid-acting insulin except FIASP (which can be substituted as needed) with up to 60 IU per day (no use of insulin supplements by pen injector allowed)
- Patient able to receive and understand study information, give written informed consent, and easily participate in the study

4.3.2 Non-inclusion criteria

Patients were not to participate in this clinical study if they met at least one of the following criteria:

- Patient already participating in another study
- Patient under the protection of the court or under guardianship or curatorship
- Patient requiring a daily dose of insulin greater than 60 IU per day
- Patients unable to continue using an insulin pump for reasons such as: severe psychiatric disorders, rapid progression of ischemic or proliferative retinopathy prior to laser treatment, exposure to magnetic fields)
- Patient allergic to nickel or adhesive
- Patient not affiliated to a social security system
- Pregnant and breastfeeding women
- Or any other criteria as determined by the investigator

4.4 EVALUATION CRITERIA

4.4.1 Primary endpoint

The primary endpoint is the estimation of HbA1c from the mean of glucose measurements over the last 10 weeks of follow-up.

Blood glucose levels were obtained from the measurements of the FreeStyle Libre continuous glucose sensor, extracted from the application provided by the manufacturer (already used in routine) and reported by the investigator in the eCRF. The investigator was asked to print the measurements from the software to facilitate monitoring of the reported data.

There will be no recalculation of the estimated HbA1c.

We have chosen to evaluate HbA1c obtained from a sensor measurement which is a good estimate of the average blood glucose level. The evolution of the classical HbA1c level is not informative on the time spent in hyper or hypoglycemia (whether or not the latter is symptomatic) because it does not reflect glycemic variability. In addition, the Nathan study highlights the reliability of estimating HbA1c over 14 days of continuous sensor measurements, as do the 2017 ADA Recommendations; more recently, the 2019 International Consensus on Time in Range recommendations reiterate the limitations of the HbA1c

criterion in the laboratory. The evolution of the monitoring of the effectiveness of insulin treatment is moving more and more towards average blood glucose and "Time in Range" (time spent in the target range/target values).

We propose to evaluate, as a secondary endpoint, the evolution of HbA1c measured in the laboratory from a blood sample at the beginning and at the end of the study, as well as the Time in Range which is automatically calculated from the data of the FreeStyle Libre reader.

4.4.2 Secondary endpoints

The secondary endpoints were:

- HbA1c:
 - Value measured in the laboratory from a blood sample taken before the D0 visit and just before the 3-month visit
- Glucose Level Measurements
 - Average of glucose measurements over each time period and over the entire study duration
 - Minimum and maximum values
 - Time in range expressed as a %.

These values were automatically calculated by the FreeStyle Libre software and will be reported by the investigator.

- Glycemic events
 - Number of symptomatic and non-symptomatic hypoglycemic events during the evaluation period, broken down by severity level
 - Number of symptomatic and non-symptomatic hyperglycemia events over the evaluation period, broken down by severity level

This information was derived from the Free Freestyle data and the data entered by the patient in the MDP.

The definition of hypoglycemia and hyperglycemia is the ADA consensus definition:

Table 1—Summary of consensus definitions			
Outcome	Definition		
Hypoglycemia	Level 1: glucose <70 mg/dL (3.9 mmol/L) and glucose \geq 54 mg/dL (3.0 mmol/L) Level 2: glucose <54 mg/dL (3.0 mmol/L) Level 3: a severe event characterized by altered mental and/or physical status requiring assistance		
Hyperglycemia	Level 1—elevated glucose: glucose $>$ 180 mg/dL (10 mmol/L) and glucose \leq 250 mg/dL (13.9 mmol/L) Level 2—very elevated glucose: glucose $>$ 250 mg/dL (13.9 mmol/L)		
Time in range	Percentage of readings in the range of 70–180 mg/dL (3.9–10.0 mmol/L) per unit of time		

- Device tolerance
 - Local skin tolerance at the pump site (adhesive hold) and at the FreeStyle Libre blood glucose sensor site (adhesive hold)
 - Any local or systemic safety issues were to be reported during the study, including the additional one-month phase at the end of the study for patients in the Omnipod group
- Incidents with devices
 - Any type of incident involving the operation of the medical devices used, especially for pumps: pulling out, control problems, transmission difficulties, occlusion, leakage, etc.
- Patient satisfaction
 - Self-questionnaire evaluating satisfaction with the use of the device (pump + PDM)

- Final question regarding patient preference between the Medtrum device and the Insulet device
- Insulin treatment
 - The insulin treatment used should be documented
 - The delivered insulin doses were obtained from the pump data record. The total volume and the distribution between basal and bolus as well as the evolution of these doses during the study will be observed.
 - Although not allowed in the study, possible additional insulin injections with a pen were documented when appropriate.

Source data	Bypass rule	Label	Format
Dates of inclusion	INC_D = (Date of last inclusion - date of first inclusion+1) / 30.44	Duration of inclusion (in months)	Digital
Inclusion and visit dates	STUDY_D = (Date of last patient follow-up - date of first inclusion+1) / 30.44	Duration of the study (in months)	Digital
Patient eligibility and randomization	ITT_D = -1 if the patient meets the inclusion and non- inclusion criteria and has used the pump device at least once -0 otherwise	Population ITT	0 = "No 1 = "Yes
ITT_D and major protocol deviation	PP_D = -1 if the patient belongs to the ITT population without major deviation from the protocol -0 otherwise	Population PP	0 = "No 1 = "Yes
Randomization	SAFT_D = -1 if the patient has used the pump device at least once -0 otherwise	Tolerance population	0 = "No 1 = "Yes
Pre-inclusion date and date of birth	AGE_D = (Pre-Entry Date - Date of Birth) / 365.25	Age (in years)	Digital
Date of pre- inclusion and date of discovery of diabetes	DIAB_D = (Pre-inclusion date - date of discovery of diabetes) / 365.25	Time since discovery of diabetes (in years)	Digital
Time since discovery of diabetes (in years)	DIAB_3CL = -0 if DIAB_D <5 -1 if DIAB_D = [5 ; 10[-2 if DIAB_D = >10	Time since discovery of diabetes (in classes)	0 = "Less than 5 years 1 = "Between 5 and 10 years

4.4.3 Calculated/derived criteria

			2 = "More than 10 years
Number of years and months of treatment per pump	PUMP_D = Number of years * 12 + number of months	Time since starting pump therapy (in months)	Digital
Weight (kg) and height (cm)	BMI_D = (weight/height ²)*10000	Body Mass Index (BMI)	Digital
IMC_D	IMC4CL_D = -0 if BMI_D<18.5 -1 if BMI_D = [18,5 ; 25[-2 if BMI_D = [25; 30[. -3 if BMI_D >= 30	BMI (in classes)	0 = "Less than 18.5 1 = " [18,5 ; 25[" 2 = " [25 ; 30[" 3 = "Greater than 30
Tolerance variables	AL_PBTOL_D = -1 if the patient reported during the follow-up an irritation/itching problem or a redness problem or another adverse event -0 otherwise	Patient with at least one tolerance problem	0 = "No 1 = "Yes
HbA1c value measured in the laboratory at D0 and 3M	EVOL_HBA1C_D = HbA1c at M3 - HbA1c at D0	Evolution of HbA1c between D0 and 3M	Digital
Estimated HbA1c (FSL) (%)	EVOL_eHbA1c = HbA1c estimate at V2 - HbA1c estimate at D0 (will also be calculated for V3 and V4)	Evolution of HbA1c estimation between D0 and V2,V3,V4	Digital
Average blood glucose at different follow-up times	EVOL_GLYC_V2 = Average blood glucose at V2 - Average blood glucose at D0 (will also be calculated for V3 and V4)	Evolution of the average blood glucose level between D0 and V2, V3, V4	Digital
Average daily basal dose at different follow-up times	EVOL_BASAL_V2 = Average daily basal dose at V2 - Average daily basal dose at D0 (will also be calculated for V3 and V4)	Evolution of the average daily basal dose between D0 and V2, V3, V4	Digital
Average daily bolus dose at different follow-up times	EVOL_BOLUS_V2 = Average daily bolus dose at V2 - Average daily bolus dose at D0 (will also be calculated for V3 and V4)	Evolution of the average daily bolus dose between D0 and V2, V3, V4	Digital

Number of Boluses/day at different follow-up times	EVOL_NB_BOLUS_V2 = Number of Boluses/day at V2 - Number of Boluses/day at D0 (will also be calculated for V3 and V4)	Evolution of the number of Bolus/day between D0 and V2, V3,V4	Digital
Time of wearing the FSL	PORT_70sup = -1 wear time greater than 70%. -0 otherwise	FSL wear time greater than 70%.	0 = "No 1 = "Yes

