7.3 VISIT 1: INCLUSION VISIT WITH INFORMED CONSENT

No study-specific procedures should be performed until informed consent has been obtained from the patient.

Study procedures at Visit 1 include the following assessments:

- Provide verbal information about the study procedures and objectives as well as those presented in the package insert, and ensure that the patient has the opportunity to ask questions
- Obtaining the signature of the informed consent
- Collect the following data using the eCRF:
 - Socio-demographic data
 - Age of diabetes, type, age of insulin therapy
 - HbA1C at the time of insulin pump prescription
 - Current model of pump used by the patient
 - Patient satisfaction with the current pump
 - Type of insulin used
 - Last HbA1C value less than one month old
 - Available glucose measurements (average of glucose measurements, estimated HbA1c, time in range)
 - Number of major glycemic events in the past month (as defined by the ADA) and in the past 6 months
 - Randomization of the patient in the pump group "Omnipod" or "Medtrum"

7.4 VISIT 2 (4 WEEKS): FOLLOW-UP VISIT AFTER 4 WEEKS OF PUMP USE.

- Collect tolerance data and possible adverse events, and report them as required from the eCRF
- Verify the conditions of use of the devices by the patient

- Collect time-stamped records of glucose values (as well as HbA1c estimated from average glucose measurements) and glycemic events, hypoglycemia and hyperglycemia, and insulin doses administered, from software provided by manufacturers
- Collect technical incidents with the device (catheter occlusion, alarms, pump detachment, pain, allergy, etc.)
- Patient satisfaction with their insulin delivery system
- Confirm or schedule the date of the V3 visit after 3 months of use
- Record all relevant data in the eCRF.

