- Description of local skin tolerance at the pump site and at the FreeStyle Libre blood glucose sensor site).
- Description of any local or systemic safety issues reported during the study, including the additional one-month phase at the end of the study for patients in the "Omnipod" arm
- Description in the total population, in each group and comparison between groups of the number of patients who had at least one tolerance problem.

❖ **Incidents with devices**

- Description of any type of incident involving the operation of the medical devices used, particularly for pumps: pulling out, control problems, transmission difficulties, obstructions, leaks, etc.
- Description in each group, in the overall population and comparison between groups

❖ Patient satisfaction

- Description of the responses to the self-questionnaire assessing satisfaction with the use of the device (pump+PDM), in each group and in the total population
- Comparison of responses between groups
- Description of responses to the final question regarding patient preference between the Medtrum device and the Omnipod device: in each group and in the total population

❖ Insulin treatment

- Description of insulin doses delivered
- Description of any additional insulin injections with a pen during the study
- Description in the total population, in each group and comparison between groups

11.2.5 Tolerance analyses:

The analyses will be performed on the tolerance population.

Prior to any analysis all DM-related incidents and DM-related tolerance will be coded by the MedDRA regulatory medical dictionary (version 20.0 or later).

A summary table (number and percentage of patients with an AE and number of events) by organ system class (OSG) and preferred term (PT) will be presented for the following categories of events by dissociating DM-related incidents and tolerance:

- According to the link (device AND procedure),
- Depending on the link (device OR procedure),
- Depending on the severity,
- Depending on the actions taken (de-pairing).

A listing of individual data will be provided describing all the information collected via the eCRF concerning the IS (including duration, resolution, severity criteria, linkage, severity etc.)

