5.2 GENERALITIES FOR STATISTICAL ANALYSIS

Depending on the nature of the criteria studied, the descriptive statistics will be as follows: For categorical data: number of individuals, number of missing values, frequency and percentages of each of the variable's terms (excluding missing data in the denominator). Twosided 95% confidence intervals will be provided when deemed appropriate. Percentage will be presented to one decimal place.

Statistical analysis of quantitative data: number of individuals, number of missing values, mean, standard deviation, median, quartiles, minimum and maximum. The data will be presented as follows: 1 decimal place more than the original variable for mean and standard deviation, 0 for median, quartiles, min and max.

Statistical analyses will be performed using SAS® software, version 9.4, SAS Institute, NC, Cary, USA.

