5.3 MISSING DATA MANAGEMENT

All incomplete study dates will be charged as follows:

- -The missing days will be replaced by 15
- -The missing months will be replaced by the month of June (06)

-Thus, if the day and month are missing, the date considered will be: 15/06/YYYY In case of calculation of duration resulting in negative values, these durations will be considered as missing.

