7.1.3 Populations of analysis

Analysis populations will be presented with the number of patients in each treatment group. Intent-to-treat (ITT) population: all included and randomized patients who used the pump device at least once.

Intent-to-treat (ITTm) population: ITT population with exclusion of the 4 patients discharged due to COVID-19.

Population Per Protocol (PP): ITT patients with no major protocol deviations.

Tolerance population: all patients who have used the pump device at least once.

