7.5 ANALYSIS OF TOLERANCE DURING THE STUDY

Analyses will be performed overall and by pump group on the **tolerance population**. Prior to any analysis, all DM-related incidents and DM-related tolerance will be coded by the MedDRA regulatory medical dictionary (version 20.0 or later).

The number of patients who had at least one tolerance problem will be described. The following criteria will be described for each period and by pump group:

- Irritation/itching (yes; no)
 - If yes, maximum intensity (low; moderate; intense)
- Redness (yes; no)
 - If yes, maximum intensity (low; moderate; intense)
- Other adverse events (yes; no)
 - All other events related to tolerance will be given in a listing.

A summary table (number and percentage of patients with AEs and number of events) by organ system class (OSG) and preferred term (PT) will be presented for the following categories of events by dissociating incidents and tolerance related to the medical device:

- According to the link (device AND procedure)
- According to the link (device OR procedure)
- Depending on the severity
- Depending on the actions taken (de-boosting)

A listing of individual data will be provided describing all the information collected via the eCRF concerning the AE (including duration, resolution, severity criteria, linkage, severity etc.)

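### AL_PBTOL_D counts patients with no tolerance assessment and no reported event as problem-free; if any such patients exist, the composite tolerance rate is biased downward

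*SAP*

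**What the plan says.** - **Derivation.** The table in SAP 4.4.3 defines AL_PBTOL_D as "1 if the patient reported during the follow-up an irritation/itching problem or a redness problem or another adverse event -0 otherwise" (the dash before the 0 is a list mark). The permitted values are 0 and 1 only.
- **Denominator.** SAP 7.1.3 defines the tolerance population as "all patients who have used the pump device at least once". No post-baseline assessment is required.
- **Missing values.** For categorical data, SAP 5.2 asks for the number of missing values and for "frequency and percentages of each of the variable's terms (excluding missing data in the denominator"). SAP 5.3 opens with "All incomplete study dates will be charged as follows" and deals only with dates and negative durations. The only other imputation rule, in SAP 7.4.1, is for the primary endpoint.
- **Use.** SAP 7.5 states: "The number of patients who had at least one tolerance problem will be described". It also lists irritation/itching, redness and other adverse events as yes/no items for each period and pump group. Protocol 11.2.4 goes further: "Description in the total population, in each group and comparison between groups of the number of patients who had at least one tolerance problem".
- **Collection.** The first scheduled tolerance collection after randomization is V2 at 4 weeks (Protocol 7.4): "Collect tolerance data and possible adverse events, and report them as required from the eCRF". Protocol 7.1 and 7.2 list no early-withdrawal visit.
- **Known exits.** SAP 7.1.3 defines ITTm as "ITT population with exclusion of the 4 patients discharged due to COVID-19". No matching exclusion is stated for the tolerance population.

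**The concern.** Irritation/itching and redness are asked as yes/no questions. A patient who was never asked, and who volunteered nothing, has an unknown answer. The derivation turns that unknown into a No and keeps the patient in the denominator. The safeguard in SAP 5.2 cannot act, because the composite has no missing category. Its Missing row in the SAP section 8 table template would always show zero.

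The composite then disagrees with its own components. In the by-period items the patient is missing; in the flag built from those items the patient is a No. Since the protocol plans to compare this count between pumps, an unequal share of unassessed patients would distort that comparison.

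**Working it through.** The plan states no expected tolerance rate, so there is no figure of its own to reproduce on this point.

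**1. What the rules do to individual records**

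| Record | By-period items (SAP 7.5 with 5.2) | AL_PBTOL_D |
|---|---|---|
| No problem at V2 or V3 | No, No | 0 |
| Redness at V2, left before V3 | Yes, missing | 1 |
| Left before V2, skin reaction volunteered and entered | Depends on the eCRF | 1 |
| Left before V2, nothing reported | Missing, missing | 0 |

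Only the last record is miscoded.

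**2. Size in the overall rate**

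Inputs from the documents: 100 patients included (SAP 5.1) and 4 COVID-19 exits (SAP 7.1.3). Assumed: the true rate p; the share u with neither an assessment nor a report; that all 100 used the pump; and that unassessed patients have the same true rate as the rest.

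Coded rate = p × (1 − u); understatement = p × u.

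If all 4 exits were unassessed, u = 4/100 = 4%:
- p = 20%: 0.20 × 0.96 = 19.2%, low by 0.8 points
- p = 30%: 0.30 × 0.96 = 28.8%, low by 1.2 points
- p = 40%: 0.40 × 0.96 = 38.4%, low by 1.6 points

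For larger assumed shares at p = 30%, u = 10% gives 27.0% and u = 20% gives 24.0%. The 20% in SAP 5.1 is an allowance for major deviations, missing data and loss to follow-up together, so it is not an estimate of u.

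Without assuming any p, recoding all 4 from 0 to 1 moves the overall rate by 4/100 = 4 points at most.

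**3. Size in the comparison**

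With equal true rates, the spurious difference is p × (difference in u between arms). Allocation is 1:1, so assume about 50 per arm.
- All 4 in one arm: u = 4/50 = 8% against 0; at p = 30%, 0.30 × 0.08 = 2.4 points, favouring whichever arm they were in.
- Two in each arm: 4% against 4%, so no spurious difference.
- Assumed u of 10% against 2%: from 0.10 × 0.08 = 0.8 points (p = 10%) to 0.40 × 0.08 = 3.2 points (p = 40%).

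The arm with the larger u loses more in relative terms, but not always in points: 10% × 10% = 1.0 point, while 40% × 5% = 2.0 points.

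**4. Length of follow-up**

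The derivation does not say whether V4 counts as follow-up. Only Omnipod-arm patients have V4, and they spend that month on the Medtrum pump. At an assumed constant monthly risk of 10%, with every patient taking the extra month, the cumulative rate goes from 1 − 0.9³ = 27.1% to 1 − 0.9⁴ = 34.4%. The 7.3-point difference is larger than most of the coding effects above.

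**5. Whether simple exclusion is enough**

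Suppose p = 20% throughout and 10% leave before any assessment. All problems among those leavers are captured as reports (2% of the total) and the other 8% are silent. The true rate is 20.0%. Excluding the silent 8% gives 0.20/0.92 = 21.7%, which is too high. Counting them all as 0 gives 20.0%; counting them all as 1 gives 28.0%. The true value lies within those bounds, but the exclusion estimate alone misses it.

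**The case against.** The strongest reply is that using every exposed patient as the denominator for reported events is a usual safety convention. The protocol also works to capture those events. Section 6.4 asks for adverse events to be documented when a patient withdraws, and section 13.2.1 has the physician enter device-related tolerance incidents that are seen or volunteered at any time. A patient who leaves because of a skin reaction and says so is coded 1, correctly. This stands, and it limits the problem to silent exits. It does not supply an answer to a yes/no question that was never put. Whether the eCRF collects the skin items at an early exit cannot be seen from the documents.

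A reader might infer that this flag is the only patient-level view of tolerance and that the gap would be invisible. The documents do not support that. SAP 7.5 also gives the by-period items and a count of patients with events by system organ class and preferred term. The SAP 5.2 missing count applies to the items, and SAP 7.2 reports reasons for not completing the study. Only the composite hides the gap.

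**Conclusion.** The point holds as a conditional defect in the derivation. As written, the rule counts an unassessed patient with no report as a No, and nothing else in the SAP corrects it. Any resulting error in the composite rate is downward and equals p × u. Using the only exit count in the documents, it is 1.2 points at an assumed p of 30%, if all 4 exits were unassessed and had the same risk as the others. It is zero if every patient had an assessment or a report.

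A reader might go further and conclude that tolerance rates are in fact understated, and in favour of the sponsor's pump because only that arm changes device. The documents do not show this. They give no number of unassessed patients and neither the arm nor the timing of the exits. The malfunction reason for withdrawal in Protocol 6.4 covers any study device, not only the Medtrum pump. The comparison is distorted if the unassessed share differs by arm, but the direction cannot be known.

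**What to change.** In SAP 4.4.3, redefine AL_PBTOL_D:
- 1 if any irritation/itching, redness or other event was recorded;
- 0 only if at least one post-baseline tolerance assessment was completed and no event was recorded;
- missing otherwise.

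Apply the SAP 5.2 denominator and report the number missing by arm. Add two sensitivity rows, one counting all missing patients as 0 (the current coding) and one counting them all as 1. For the between-group comparison, define follow-up as V1–V3 and describe V4 separately.

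The cost is a change to one derivation and a few table rows, with no new data. The denominator becomes slightly smaller, and exclusion alone can slightly overstate the rate, which is why both bounds are needed. If nobody is unassessed, the recoding changes no result and the table shows that.
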